The results of our clinical trial could offer a simple and low-cost intervention to help avert serious respiratory complications in sickle-cell disease that could lead to important reductions in morbidity and death in children with sickling disorders and to major changes in the management of their vitamin D status.

4. General investigational plan

Acute respiratory illness is a principal cause of morbidity and mortality worldwide¹⁷ and can be devastating for children with sickle cell disease, an inherited red blood cell disorder affecting an estimated 100,000 Americans,³ predominantly of African ancestry. Sickle cell disease is characterized by a shortened life expectancy, hemolytic anemia, acute episodes of vaso-occlusive pain, and recurrent, chronic damage to vital organs.^{3, 4} Pulmonary manifestations are common and often severe. Respiratory infections or asthma attacks that would have no lasting effects in individuals with no sickle hemoglobinopathy can trigger severe or even fatal manifestations in those with sickle cell disease.¹⁸ For instance, children with influenza and sickle cell disease are hospitalized at a rate more than 50-fold greater than children without sickle cell disease.¹⁹ Asthma is common, affecting 15 to 28% of children with sickling disorders.⁵ Unique to sickle cell disease is a respiratory complication characterized by fever, respiratory symptoms and a new pulmonary infiltrate, known as "acute chest syndrome."⁶ Commonly precipitated by respiratory infections and asthma, the acute chest syndrome is the leading cause of death in sickle cell disease.^{5, 6} The pathogenesis of sickle cell lung disease is unclear, but involves microvascular occlusion, hemolysis-induced endothelial dysfunction and vasculopathy that produce a chronic inflammatory state, often exacerbated by an infectious trigger.^{3, 20, 21} Compromised immunity from functional asplenia may contribute to the risks of respiratory infections and pulmonary disease.²² Improved vaccination and penicillin prophylaxis have greatly reduced the risk of bacterial pathogens but are ineffective against viruses and atypical organisms that now predominate as risks for acute chest syndrome.²³

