validated questionnaire administered biweekly. Analysis included 62 children, mean (SD) age 9.9 (3.9) years, 32 (52%) females, predominantly HbSS (87%), with mean baseline 25-hydroxyvitamin D of 14.3 ng/mL. The mean (SEM) 25-hydroxyvitamin D concentrations during Treatment Years 1 and 2 are shown in Figure 2. A total of 291 adverse events were reported, including 55 serious adverse events in 20 subjects, most of which were expected for sickle cell disease; none were attributed to the study drug. There were 17 abnormal safety laboratory values; all abnormal laboratory values were determined to be clinically insignificant, without requiring withholding or discontinuation of study treatment.

The annual rates of respiratory events at baseline, intervention year-1, and year-2 with the high-dose were 4.34 ± 0.35 (SEM), 4.28 ± 0.36 , and 1.49 ± 0.37 , and, with the standard-dose, 3.91 ± 0.35 , 3.34 ± 0.37 , and 1.54 ± 0.37 , respectively (see Figure 1 above). In pediatric patients with sickle cell disease, two-year monthly oral vitamin D3 was associated with a >50% reduction in the rate of respiratory illness during the second year, with similar decreases from high- and standard-dose treatment.

In summary, in children and adolescents with sickle cell disease who received monthly bolus doses of oral vitamin D₃ under observation for two years, the annual rates of respiratory events (respiratory infections, asthma exacerbations and acute chest syndrome) decreased by more than 50% during the second year of treatment, with similar reductions in the groups treated with 100,000 IU/month and with 12,000 IU/month. The treatment groups did not differ significantly with respect to pulmonary function, hand-grip strength, fever or episodes of vaso-occlusive pain. Both doses were safe with no significant differences in adverse events.

[figure not shown]

Figure 2: Mean serum 25-hydroxyvitamin D concentrations by treatment group: High-dose: 100,000 IU (2.5 mg) vitamin D₃ given once a month under observation (daily equivalent 3,333 IU/day); Standard-dose, 12,000 IU (0.3 mg) vitamin D₃ given once a month under observation (daily equivalent 400 IU/day).

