Reporting of adverse events: All identified Adverse Events will be reported to the Sponsor-Investigator. The Sponsor-Investigator will determine whether the event is *serious* or an *Unexpected Suspected Adverse Reaction* and requires expedited reporting. Serious Adverse Events (SAEs) that meet criteria for FDA and/or CU IRB reporting, i.e., unexpected, suspected to be related to study drug (FDA requirements), or unanticipated problems (CU IRB requirement) will be reported within 24 hours to the Sponsor-Investigator for review. Other SAEs that do not meet the above criteria will be reviewed by Clinical Trial Safety Officer with reports to the Sponsor-Investigator quarterly. The Sponsor-Investigator must also report SAEs that meet criteria for FDA and/or CU IRB reporting to the DSMB promptly within one week, while other SAEs that do not meet the above criteria will be reported to the DSMB Chair quarterly. The Sponsor-Investigator is required to report to the FDA serious, unexpected, suspected adverse event within 15 days, and within 7 days if fatal. A serious, unexpected suspected adverse reaction is a serious adverse event not previously observed with the drug and that has a reasonable possibility of having been caused by it. The CU IRB requires reporting of all Unanticipated Problems promptly and not later than one week, as well as during continuing annual review. An Unanticipated Problem is defined as any incident, outcome or experience involving risks to subjects or others in any human subject research that is unexpected, related or possibly related to research participation, and suggests that the research places subjects or others at a greater risk of harm (physical, psychological, economic or social harm) than was previously known or recognized. Adverse Events that do not meet the criteria of a SAE will be reported the DSMB during biannual review.

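### A death judged unrelated to study drug reaches the DSMB Chair only in the quarterly report, up to about 91 days later instead of 7

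*Combined protocol and SAP*

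**What the plan says.** Under Data and Safety Monitoring, the paragraph Reporting of adverse events sets two routes for SAEs.

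- **Fast route.** It covers events that are "unexpected, suspected to be related to study drug (FDA requirements), or unanticipated problems (CU IRB requirement"). These go to the Sponsor-Investigator within 24 hours, and the Sponsor-Investigator must "report SAEs that meet criteria for FDA and/or CU IRB reporting to the DSMB promptly within one week".
- **Slow route.** All remaining SAEs are reviewed by the Clinical Trial Safety Officer and passed to the Sponsor-Investigator quarterly. On the DSMB side, "other SAEs that do not meet the above criteria will be reported to the DSMB Chair quarterly".

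The same paragraph defines the criteria. The FDA category "is a serious adverse event not previously observed with the drug and that has a reasonable possibility of having been caused by it". The IRB category is an incident that is "unexpected, related or possibly related to research participation, and suggests that the research places subjects or others at a greater risk of harm" than was known before.

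Fatal events are mentioned once: "The Sponsor-Investigator is required to report to the FDA serious, unexpected, suspected adverse event within 15 days, and within 7 days if fatal". That is a report to the FDA, not to the DSMB.

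The DSMB meets bi-annually. The paragraph on its review allows additional safety reviews if needed, without saying what would prompt one.

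**The concern.** The speed at which the DSMB hears of a death depends entirely on a case-level judgement of relatedness. In this trial that judgement will tend to point to the disease. Section 4 says that "the acute chest syndrome is the leading cause of death in sickle cell disease", and the SAP counts acute chest syndrome in the primary endpoint. The ViDAS-1 summary in Section 4 reports 55 SAEs in 20 subjects, "most of which were expected for sickle cell disease; none were attributed to the study drug".

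The trial also compares two schedules of the same vitamin, and the plan expects Year 1 event rates under the monthly control to resemble those under placebo. If the study hypothesis is right, a disadvantage in one arm would show as weaker protection against respiratory complications, not as drug toxicity. A fatal respiratory event could then be attributed to the disease in good faith and still be the kind of event that an independent board should see early.

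**Working it through.** The plan gives no statistical figure to reproduce. The check follows a death through the reporting rules and then compares the time limits.

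**Step 1. Does a death judged unrelated meet the FDA criterion?** The definition joins two conditions with *and*: not previously observed with the drug, and a reasonable possibility of causation. The list that opens the fast route separates its first two terms only by a comma and could be read as alternatives, but the later definition settles that both are needed. A death judged unrelated fails the second condition.

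**Step 2. Does it meet the IRB criterion?** That definition needs three things together: unexpected, at least possibly related to taking part in the research, and suggestive of greater risk. A death judged unrelated fails the second.

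**Step 3. Does another rule catch it?**

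| Provision | Why it does not apply |
|---|---|
| Seven-day limit for fatal events | Report to the FDA; covers only unexpected, suspected events |
| All adverse events go to the Sponsor-Investigator | No time limit; does not reach the DSMB |
| More frequent DSMB reviews if needed | A death is not named as a trigger |
| Considerations for early termination | Mortality is not named; only the open-ended last item could cover it |

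The death therefore takes the slow route.

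**Step 4. How long is the lag?**

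- One quarter: 365.25 / 4 = 91.3 days.
- Fast route to the DSMB: 7 days.
- Difference if only one quarterly cycle applies: 91.3 − 7 = 84.3 days.
- If the quarterly report to the Sponsor-Investigator and the quarterly report to the Chair follow one another unsynchronised: 2 × 91.3 = 182.6, or about 183 days.

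The documents do not say whether the two cycles are aligned, so the maximum lies between about 91 and 183 days. Visits are monthly, so one quarter covers up to three further visits per participant. These are upper limits: a death shortly before a report falls due would be seen sooner.

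**Step 5. How likely is the slow route?** In ViDAS-1, 0 of 55 SAEs were attributed to study drug. On that experience almost every SAE would go quarterly. The figure describes SAEs in general. The ViDAS-1 summary mentions no deaths, so it gives no death rate.

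**The case against.** The strongest reply is that nothing in the plan is broken. The two routes are stated clearly, no provisions conflict, and a one-week DSMB notice for every death is not a requirement the documents set for themselves. The Safety Officer reviews the slow-route SAEs, the DSMB may hold extra reviews and consider other matters, and participants can be identified to it where there is a safety concern. Where relatedness is uncertain, the IRB wording extends to events that are possibly related, so a doubtful case that is also unexpected and suggests greater risk would go within a week.

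Much of this stands. It makes the point a matter of design and limits it to deaths judged unrelated. It does not close the gap: no death-specific trigger is stated, and the DSMB cannot call a review over a death it has not been told about.

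Stronger readings that the documents do not support:

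- *That a death from acute chest syndrome takes the slow route because it is expected in this disease.* The FDA definition ties unexpectedness to the drug, so being common in the disease does not by itself make such a death expected. The ViDAS-1 remark about events expected for sickle cell disease describes past results and is not the reporting rule here. Relatedness is the main path.
- *That the Sponsor-Investigator would know at once while the DSMB waits.* The plan does not say so. The 24-hour rule covers only qualifying SAEs; the others reach the Sponsor-Investigator quarterly.
- *That unexpected, suspected deaths are also delayed.* They are not. They go to the DSMB within one week and to the FDA within 7 days.

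**Conclusion.** The point holds for deaths judged unrelated to study drug. Followed as written, the rules allow the DSMB Chair to learn of such a death up to about 91 days afterwards, or up to about 183 days if the two quarterly steps run in sequence, against 7 days for a qualifying SAE. The full board, which meets bi-annually, could see it later than its Chair.

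Two assumptions carry this. The 183-day figure assumes unsynchronised quarterly cycles. The view that a fatal respiratory event would probably be judged unrelated rests on the disease background and on the ViDAS-1 attributions, not on any observed deaths. A separate DSMB charter might already cover deaths, but none is among these documents.

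The point affects safety oversight only. It has no bearing on the sample size, the analysis or the validity of the primary comparison, and it ranks as a minor, inexpensive improvement.

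**What to change.** Amend both quarterly sentences in Reporting of adverse events:

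1. **To the Sponsor-Investigator:** every death, whatever its expectedness or relatedness, is reported within 24 hours.
2. **To the DSMB:** every death, whatever its expectedness or relatedness, is reported to the Chair within one week.

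State when each period starts, for example when study staff first learn of the death. Keep the quarterly route for other SAEs. Changing only the DSMB sentence would not be enough: the Sponsor-Investigator might not yet have the report when the one-week limit ran out.

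Both limits already exist in the plan for qualifying SAEs, so no new procedure is needed. The cost is a short protocol amendment and one prompt notification per death. Blinding, endpoints and sample size are untouched.

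Life-threatening SAEs could be added on the same terms. That would bring some extra notifications, and the documents give no count from which to estimate how many, so it should be a separate decision.

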- 4) Current diagnosis of rickets
- 5) History of hypercalcemia or diagnosis of any medical condition associated with hypercalcemia, including primary hyperparathyroidism, malignancy, sarcoidosis, tuberculosis, granulomatous disease, familial hypocalciuric hypercalcemia
- 6) Current use of corticosteroids, excluding inhaled steroids
- 7) Current use of anticonvulsants (phenytoin, phenobarbital, carbamazepine)
- 8) Therapy with thiazide diuretics or lithium carbonate
- 9) Known liver or renal disease
- 10) Patients taking medications for pulmonary complications of sickle cell disease not on a stable dose of medications, as defined by a change in medications or doses within the three months prior to study entry
- 11) Patients on chronic red blood cell transfusion therapy
- 12) Pregnancy

Subject Justification:

This study will enroll about 80 children and adolescents, ages 3-20 years, with sickle cell disease. Participation of children in the proposed research is essential to answer the research question, because pulmonary complications in sickle cell disease develop early in life. The study aims to determine whether vitamin D supplementation can reduce the risk of respiratory complications during childhood and prevent deterioration in lung function. The proposed research will predominantly include subjects of African origin, including African Americans and those from the Caribbean Islands (Dominican Republic, Puerto Rico, West Indies, Cuba, and Haiti), because sickle cell disease primarily affects people of African descent.³

Subject Randomization:

Within one month after screening procedures have been completed, subjects will be randomized. Using computer-generated randomization, participants with 25-hydroxyvitamin D concentrations of 5-60 ng/mL will be randomly assigned using randomly permuted blocks of size 2, 4 or 6 assignments with separate schema prepared for stratification by age (3-9 and 10-20), gender and hydroxyurea therapy. Randomization will be performed by the Research Pharmacy; all other research staff and participants will be blinded to allocation.

Subject Compensation:

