Our primary study analysis will examine the annual rate of respiratory events (the sum of respiratory infections, asthma exacerbations and episodes of acute chest syndrome) in children with sickle cell disease randomized in a double-blind manner to the daily and monthly doses of oral vitamin D₃. The primary statistical analysis will be by "intention to treat" and will use a semiparametric regression method to estimate the between group difference in intensity (events per subject per unit of time at risk) with the assumption that covariates have a multiplicative effect on the mean and rate functions. This approach takes account of the skewed distribution of the respiratory events. The results of this analysis will be summarized as a regression parameter estimate, with the standard error of the estimate, a chi-square test with associated p-value, and a hazard ratio with confidence limits expressing the rate difference of the daily relative to the monthly group (as described in Lin, DY, Wei, LJ, Yang, I, and Ying, Z. "Semiparametric regression for the mean and rate functions of recurrent events," *J R Stat Soc Series B Stat Methodol*, 2000; 62:711–730).⁶³ This approach can adjust for group differences in time-independent covariates and estimate rate ratios at specific values of covariates and at specific times of follow up. The annualized rate of events and the average inter-event interval (in two-week intervals, the observation protocol) will be entered as time-independent covariates. After testing the initial hypothesis of overall group difference, we will sequentially test the between-treatment group differences in the study design enrollment criteria strata: age, gender and therapy (hydroxyurea). Secondary analyses using the same statistical framework will separately test the study hypotheses at the one-year time point. The functional form of covariates and proportional hazards assumptions will be checked for all models and cumulative hazard plots and cumulative residual plots will be used to display group differences in the evolution of events and model fit, respectively.

Subsidiary analyses will be made to examine a number of secondary study hypotheses with respect to the effects of vitamin D₃ on changes in pulmonary function and airway inflammation, and on immune system, but these comparisons have not entered into the sample size calculation. Data will be summarized as means \pm standard

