deviation or as counts and proportions. Study Group differences in continuous measures at baseline will be compared using independent *t* tests and differences in dichotomous categorical measures at baseline will be compared using Fisher's exact test.

Sample size

For sample size estimation, we base our estimate of the annual rate of respiratory events on the rate observed in the earlier ViDAS-1 trial in our study population, a mean annual baseline respiratory event rate of 4.1. For our estimate of the treatment effect, we use the observed reduction in annual mean respiratory event rate in the earlier ViDAS-1 trial for *monthly* bolus oral vitamin D3, 100,000 IU/mo (2.5 mg/mo), from Treatment Year 1 to Treatment Year 2 from 4.28 ± 0.36 (SEM) to 1.49 ± 0.37 , or a decrease of about 65 percent. Using a conservative estimate of a treatment effect of 50 percent reduction in the rate of respiratory events as the minimal *clinically* significant difference to be detected, **26 subjects in each group will be sufficient to detect an effect size of this magnitude with a two-sided significance level of alpha = 0.025 and 90 percent power. Allowing for as much as a 15 percent loss of participants during the two-year study (due to clinical events, such as initiating chronic red blood cell transfusion therapy, failure of compliance or exclusion or withdrawal for any reason), then our sample size estimate is $26/0.85 = 31$ participants in each treatment group, or a total of 62 participants.** Although the secondary analyses planned have not entered into the calculation of the sample size required for the proposed study, the conservative specification for the treatment effect; 90 percent power; and a generous allowance for loss of participants, should help provide adequate power for subsidiary comparisons.

Annualized Event Rate and Inter-Event-Interval (IEI)

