All primary and secondary outcome analyses will be performed under the intent-to-treat principle. Crude estimates of group differences in the annualized event rate and average inter-event-interval during Treatment Year 1 and Treatment Year 2 will be analyzed by linear mixed models for repeated measures with fixed effects for group, time and group-by-time interaction, and an AR(1) covariance structure. Analyses of secondary outcomes for pulmonary function testing will also use this approach. Further analysis of treatment group differences will be assessed using a variation of the Cox Proportional Hazards model with a counting process input of start and stop times for each event and the robust sandwich covariance estimator of Lin.⁶³ This approach models hazard for recurrence under the assumption of proportional mean processes and generates hazard ratios with 95% confidence intervals and Wald Chi-Square statistics for testing the null hypothesis. We will evaluate the influence of the event rate, average IEI as covariates and calculate between treatment group hazard ratios. We will also evaluate the influence of randomization stratifying variables as covariates of the estimate of the between treatment group difference: sex (female vs male), age (child vs adolescent) and hydroxyurea use (use vs non-use). For participants in each treatment group who withdraw from the study prior to completion of the protocol, we will repeat the primary intent-to-treat analysis with the subset of participants who completed the two-year study in a "per protocol" analysis. Finally, treatment group differences in adverse events of least grade 2 severity will be assessed with chi-square or Fisher's Exact test. We will only present comparisons of events where three or more instances are reported over the two-year treatment period.

DATA AND SAFETY MONITORING

Adherence to protocol: Conduct of the clinical trial will be in accordance with this new protocol for the ViDAS-2 study in our Investigational New Drug application. This protocol includes the appointment of a Clinical Trial Safety Officer to review laboratory results as they become available, and the formation of a Data and Safety Monitoring

Board (DSMB) consisting of an expert in pediatric sickle cell disease, a biostatistician, and a Pediatric Endocrinologist with expertise in vitamin D metabolism. The DSMB will meet bi-annually.

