Clinical Trial Data and Safety Monitoring Board review: The Trial Statistician and Trial Epidemiologist will prepare a report for the DSMB at the end of Treatment Year 1 and Treatment Year 2. Data will be presented in a blinded fashion and study subjects will be identified only in the case of a safety concern. Biannual (and, if needed, more frequent) safety reviews will be conducted. Consideration for early termination of the trial will include: (i) failure of enrolled participants to meet entry criteria, (ii) differences in the baseline characteristics of the two study groups (despite gender- and age-stratified randomization), (iii) excessive or unbalanced loss of study participants, and (iv) other considerations to be determined by the DSMB.

Data management and quality: The Sponsor-Investigator or a designated Study Investigator will review all completed data collection forms biannually for protocol compliance and for completeness and accuracy of data. A statement of the results of this review will be included in the annual report to the FDA Orphan Products Program, in the annual IND report to the FDA, the CU IRB, and in the biannual reports to the Clinical Trial Data and Safety Monitoring Board and.

Reviews of clinical trial progress: Progress in the conduct of the clinical trial will be reviewed at least annually and more frequently as required by the FDA and the CU IRB, and biannually by the Clinical Trial Data and Safety Monitoring Board,

Records to be kept: Case Report Forms (CRF) will be provided for each subject. Subjects will not be identified by name on any study documents. After patient and subject identifiers have been replaced by study identifiers, the results of all clinical and laboratory assessments will be recorded on Case Report Forms for each subject. In a similar manner, demographic data and data from the medical history, physical examination will be recorded on Case Report Forms. All data on the Case Report Forms will be legibly recorded in black ink or typed. Corrections will be made by striking through the incorrect entry with a single line and then entering the correct information

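### Baseline differences between the arms are listed as a reason to consider ending the trial, with no threshold or purpose given; chance imbalance calls for adjustment, not stopping

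*Combined protocol and SAP*

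**What the plan says.** The Clinical Trial Data and Safety Monitoring Board review section introduces a four-item list with "Consideration for early termination of the trial will include". Item (ii) is "differences in the baseline characteristics of the two study groups (despite gender- and age-stratified randomization". The other items are enrolment of ineligible participants, heavy or uneven loss to follow-up, and anything else the board decides. The same section says of the board's reports: "Data will be presented in a blinded fashion and study subjects will be identified only in the case of a safety concern".

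Separately, the Statistical Analysis Plan tests the arms against each other at baseline, by two-sample t test for continuous variables ("Study Group differences in continuous measures at baseline will be compared using independent") and by Fisher's test for binary ones. It gives no significance level and no list of variables for these tests.

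Subject Randomization describes computer-generated permuted blocks of 2, 4 or 6, run by the Research Pharmacy with other staff blinded, and "separate schema prepared for stratification by age (3-9 and 10-20), gender and hydroxyurea therapy".

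On adjustment, the Statistical Analysis Plan says of the primary model: "This approach can adjust for group differences in time-independent covariates". Treatment Outcome Analysis adds: "We will also evaluate the influence of randomization stratifying variables as covariates".

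**The concern.** With concealed, computer-generated allocation, any difference between the arms at baseline arises by chance unless the process itself broke down. Chance imbalance puts no participant at risk and does not invalidate the comparison, and ending the trial does nothing to correct it. Item (ii) nevertheless offers it as a reason to consider ending the trial. It does not say how large a difference matters, on which variables, or whether the aim is to detect a faulty allocation.

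At stake is a trial of 62 randomised participants in an orphan disease. A board that took the item at face value could come under pressure to stop for a reason unrelated to safety or efficacy. Stopping after the Treatment Year 1 report would also lose both questions reserved for Treatment Year 2: whether any early benefit of daily dosing lasts, and whether the monthly bolus again shows a delayed reduction.

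**Working it through.** **Inputs from the documents.** Sample size section: event rate 4.1 per year, 50% reduction, two-sided alpha 0.025, 90% power, 26 evaluable per group, 15% loss, ViDAS-1 standard errors 0.36 and 0.37. General investigational plan: ViDAS-1 had 31 per arm.

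**Assumed, because the documents do not give them.** Level 0.05 for each baseline test; number of tests k from 5 to 20; common pairwise correlation ρ from 0 to 0.6.

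**Step 1: the plan's own figure.** The plan gives no figure for baseline imbalance, so the one to reproduce is the sample size. No SD is stated; from the standard error it is 0.37 × √31 = 2.06. The difference is 4.1 − 2.05 = 2.05. Then n = 2 × (2.241 + 1.282)² × 2.06² / 2.05² = 25.1, rounded up to 26. Allowing for loss, 26/0.85 = 30.6, so 31 per group and 62 in total. The stated figures reproduce.

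**Step 2: how large are chance differences at 31 per arm?** The standard error of a standardised mean difference is √(2/31) = 0.254.

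- P(difference > 0.25 SD) = 2 × [1 − Φ(0.25/0.254)] = 32%.
- P(difference > 0.5 SD) = 4.9%.

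Of ten unstratified variables, about three (10 × 0.32) would therefore be expected to differ by more than 0.25 SD under perfect randomisation. Subject Justification speaks of enrolling about 80. If all were randomised, 40 per arm, the 32% becomes 26%. None of this depends on significance tests.

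**Step 3: what if item (ii) were read as any baseline p < 0.05?** This reading is an assumption. The chance of at least one such result under correct randomisation is 1 − 0.95^k for independent tests. The correlated columns come from simulation (20,000 replicates, equal pairwise correlation).

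| Tests k | ρ = 0 | ρ = 0.4 | ρ = 0.6 |
|---|---|---|---|
| 5 | 22.6% | 20% | 16% |
| 10 | 40.1% | 33% | 25% |
| 20 | 64.2% | 48% | 36% |

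The table gives every test a true size of 5%. Fisher's exact test falls short of that: at 31 per arm its actual size is 1.0% at 10% prevalence, 2.7% at 30% and 3.0% at 50%. Ten t tests with five Fisher tests at 30% prevalence give 1 − 0.95^10 × (1 − 0.027)^5 = 48%, against 53.7% for 15 independent tests at a full 5%.

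**Step 4: where adjustment stands in the plan.** The primary analysis names the annualised event rate and the inter-event interval as covariates to be entered. It tests the overall group difference first and turns to age, gender and hydroxyurea afterwards. Treatment Outcome Analysis again evaluates the influence of those three factors. So the stratification factors are considered but are not stated to be in the model that gives the primary test. The section on DSMB review does not mention adjustment.

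**Step 5: the stratification description.** Item (ii) refers to stratification by gender and age only, as does the screening text of the Study protocol section (item iv). Subject Randomization adds hydroxyurea, and Treatment Outcome Analysis names all three factors.

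**The case against.** The strongest reply is that item (ii) triggers nothing. It is one topic in a discretionary list, put to a board that includes a biostatistician and sees data in blinded form. That is right. A reader might infer that the planned t and Fisher tests would often set off termination, with 64% as the chance. The documents do not support this. The tests appear beside the descriptive summaries, are not assigned to the board's reports, and are not mentioned in the section on DSMB review. The 64% needs 20 independent tests at 0.05. The schedule does collect more than 20 baseline measures, but the plan does not say which would be tested, and cytokines, C-reactive protein and blood counts are unlikely to be independent. Even then, the figure is the chance of one small p-value, not of stopping.

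The second reply is that a gross imbalance despite stratified randomisation can reveal an allocation or dispensing failure, and that item (ii) sits among other checks on trial conduct. That is a reasonable reading, although the text does not state it. It is a good argument for narrowing the item instead of simply deleting it.

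The third reply is that adjustment is already provided for. This is partly true: the model permits it and the stratification factors are examined. But they are examined after the overall test, and adjusting for them would not correct imbalance in other variables.

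**Conclusion.** The point holds as a low-severity matter of wording and analysis. Item (ii) makes baseline difference a ground for considering termination without threshold, variables or purpose. At 31 per arm, a difference above 0.25 SD on any given unstratified variable is expected about 32% of the time by chance alone, and stopping is no remedy. The 32% rests on correct randomisation, an approximately normal mean difference and full recruitment of 62.

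No probability of termination can be derived from the documents. The range of about 16% to 64% applies only if the board took any baseline p < 0.05 as meeting the item, over 5 to 20 tests each of true size 5%, with correlation 0 to 0.6. Conservative Fisher tests would lower it. The figures of 26, 31 and 62 and the alpha of 0.025 are unaffected.

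**What to change.** 1. In the section on DSMB review, delete item (ii) or limit it to evidence that randomisation or allocation failed, for example assignments or dispensing that do not match the randomisation schedule. The narrower form keeps a legitimate prompt for the board.
2. Add a sentence saying that chance imbalance is handled in the analysis and is not a reason to stop.
3. In the Statistical Analysis Plan, enter age group, sex and hydroxyurea use as covariates in the primary model, instead of only evaluating their influence after the overall test. Any other prognostic baseline covariate should be named in advance.
4. Make the description of stratification the same throughout; Subject Randomization includes hydroxyurea.
5. Optionally, show baseline values by arm descriptively, without p-values. This is a reporting change and alters no result.

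The cost is a few lines of text. The model gains three binary covariates. At the planned rates, Treatment Year 1 would yield about 31 × 4.1 + 31 × 2.05 = 191 events from 62 participants, so this is a modest addition. No extra participants or data are needed.
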